Recent advances in the understanding of the etiology of obesity, along with development of novel pharmaceutical and surgical treatment options have yet to contribute to a reduction in the obesity prevalence in the US population. Improving diet and physical activity are still the foundation of current obesity treatments. One approach shown to be useful in modulating energy intake to support weight loss in overweight/obese individuals is provision of pre-portioned foods and beverages (i.e., meal replacements; Cheskin 2008, Hannum 2004 and 2006, 1-Ieymsfield 2003). Indeed, a group of obesity experts has considered the evidence behind this strategy as sufficiently strong and consistent to be considered empirically proven compared to more conventional dietary advice, such as food choices based on general concepts like balance, variety, and moderation (Casazza 2013). Some commercially available weight loss programs utilize this approach; however, data from randomized clinical trials documenting the degree of weight loss achievable with these programs is often lacking.

In this context, the role of commercially-available weight loss programs has received increased attention by the scientific community (Gudzune 2015, Jensen 2014). In 2013, joint guidelines issued by the American Heart Association, the American College of Cardiology and The Obesity Society for the management of overweight and obesity in adults (Jensen 2014) examined the use of some commercial programs. The general recommendation was that some commercially available programs that promote a comprehensive lifestyle intervention can be prescribed as an option for weight loss provided there is peer-reviewed published evidence of their safety and efficacy. Yet, well designed, randomized, controlled trials directly testing efficacy of many programs have not been conducted. Thus, a need exists to identify evidence-based, commercially available weight management programs.

Two such commercially available weight loss programs are the Take Shape For Life (TSFL) Optimal Weight 5 & 1 PlanTM and the Medifast AchieveTM Plan (also known as the 4 & 2 & 1 Plan® offered by Medifast Direct). Both programs utilize portion-controlled, nutritionally balanced meal plans combined with various levels of programmatic support. The meal plans consist of either four or five Medifast meal replacements per day supplemented with purchased healthy foods (lean protein, vegetables and healthy fats) to create self-prepared lean and green meals (one or two per day, depending on the specific plan). Preparation of the lean and green meals helps teach portion control and life-long healthy eating habits. The Medifast meal replacements are nutrient dense and fortified with 24 vitamins and minerals to ensure adequate micronutrient nutrition while on a calorie restricted, reduced energy meal plan.

Both programs offer programmatic support, with varying degrees of personal support. TSFL takes a holistic approach to optimal health (and weight loss for those who need it) and provides a skilled and caring personal TSFL coach to help people restore their health and improve their quality of life (QoL). TSFL is based on the Habits of Health system (Andersen 2008) which emphasizes the importance of being physically healthy, free of stress, and poised for a more fulfilling life.

Confidential

MediJ'ast Direct (MEDD) focuses on individuals who want less support with a self-guided program that offers a variety of tools to assist in weight loss, including written and online resources, program guides, and a self-help workbook, among other items. MEDD users also have access to the optional services of the Medifast Nutrition Support Team, a group of professionals with expertise in the Medifast programs, products, and more generally, in nutrition, exercise and behavioral change. This team is available by phone or e-mail to answer programmatic, weight loss and exercise questions for both MEDD and TSFL users, as well as TSFL coaches.

The interventions in this study are designed to mimic the TSFL and MEDD user experiences and will utilize the meal plans, Medifast products, and support options available for each of these programs. The TSFL and MEDD groups will be compared to a control group following a self-directed, food-based, reduced-calorie diet consistent with the 2015 Dietary Guidelines for Americans and based on the United States Department of Agriculture (USDA) ChooseMyPlate program.

4. Objectives

The primary objective of this study is to evaluate the effects of two commercially available weight loss programs, the TSFL and the MEDD programs, each compared to a self-directed control diet, on changes in body weight over a 16-week weight loss phase, in apparently healthy overweight and obese men and women.

Secondary objectives include, examining effects of each weight loss program compared to the seli directed control diet on changes in body composition, body circumference parameters, QoL, and biomarkers of inflammation over a 16-week weight loss phase. Relationships between changes in body weight with self-reported adherence and QoL assessments will also be examined. Additionally, participant perspectives on program satisfaction and sense of health/well-being will be assessed at the end of the study.

5. Study Sample

Participants will be apparently healthy men and women, 18-65 years of age, inclusive, each with a body mass index (BMI) of 27.0 to 42.0 kg/m², inclusive. No more than 10% of participants will be enrolled with a BMI 27.0 kg/m² and <30.0 kg/nl and no more than 25% of participants will be males.

6. Study Design and Procedures

6.1. Study Design

The study will utilize a randomized, controlled, 16-week parallel study design with one screening visit (Visit I; week -I); one baseline visit (Visit 2; week 0); and five clinic visits (Visits 3, 4, 5, 6, and 7; weeks 2, 4, 8, 12, and 16).

Screening {Visit 1; week -1)

At the screening visit (Visit I; week -I), after providing informed consent, participants will undergo screening visit procedures (evaluations of demographics, medical history, inclusion and exclusion criteria, prior and current medication/supplement use, height, vital signs, and BMI

Confidential

calculation). Additionally, a gown body weight (fasted 12 ± 2 h, water only, anchored to the time of gown body weight measurement) will be measured. Fasting blood samples will be collected for a chemistry profile and hematology panel. Female participants <60 years of age will also undergo an in-clinic urine pregnancy test.

Baseline (Visit 2; week 0)

At Visit 2 (week 0), participants will arrive at the clinic fasted $(12 \pm 2 \text{ h}, \text{water only, anchored to time of gown body weight measurement) to undergo clinic visit procedures [evaluations of inclusion/exclusion criteria, concomitant medication/supplement use, vital signs, BMI calculation, and adverse events (AE)]. Gown body weight and body circumferences [waist, hip, chest, upper arm (dominant arm), and thigh (dominant leg)] will be measured. Additionally, female participants <60 years of age will undergo an in-clinic urine pregnancy test. Blood samples will be collected for analysis of high-sensitivity C-reactive protein (hs-CRP), with additional blood samples collected and archived for possible future analysis of non-genetic indicators of inflammation and metabolism. A dual energy x-ray absorptiometry (DXA) scan will be performed (female participants <60 years of age must have a negative pregnancy test before the DXA scan is initiated). Participants will then be administered the Impact of Weight on Quality of Life (IWQOL)-Lite and the RAND-36 Questionnaires (Appendices 3 and 4). Additionally, all participants will be administered the Program Questionnaire (questions I and 2 only; Appendix 5). Participants that complete all baseline testing will be randomized before 12:00 h to one of three study groups (Control, TSFL, or MEDD), as follows:$

Control Group

The Control group will follow a self-directed diet, which is a food-based, reduced-caloric diet, consistent with the 2015 Dietary Guidelines for Americans (See Supplementary Materials). The Control group will receive a one-on-one personal instruction session (10-15 min) with a trained member of the study staff at the Visit 2 (week 0) clinic visit. A personalized daily energy intake level will be determined for each participant based on a targeted weight loss goal of 7% over the 16-week weight loss phase. Participants will receive publicly available information from the USDA Choose MyPlate program. Participants will be instructed to start their weight loss program the day following randomization (day I). No weekly check-ins will occur. More details on the self-directed control diet can be found in Section 6.4.1.

TSFL Group

Participants randomized to the TSFL group will follow Medifast's TSFL Optimal Weight 5 & I Plan'". At Visit 2 (week 0), participants will be dispensed study-specific printed materials (including the "Getting Started Instructions"), along with a starter meal kit containing approximately one week's worth of study foods (see Supplementary Materials). Participants will place an order for the following four weeks' worth of study foods with additional study foods ordered throughout the study. Following Visit 2 (week 0), participants randomized to this group will receive TSFL coaching with an assigned research assistant trained to function as a TSFL coach. Coaching, for the purpose of this study, will take place via telephone. The initial session (45 min in length) will occur the day of Visit 2 (week 0) as participants will be instructed to start their weight loss program on the day following the randomization visit (day I). Coaching sessions (i.e., phone consults) will occur at additional times throughout the 16 weeks.

Participants in the TSFL group will be encouraged to track weight and food intake, discuss their

Co,?fldentia/

progress with their coach during the coaching sessions, and access TSFL written, online, and virtual support tools, to use at their discretion. To be consistent with the commercially available program, participants with questions that the TSFL coach cannot address will be referred to the Medifast Nutrition Support Team. More details on the TSFL program can be found in Section 6.4.1.

MEDDGroup

Participants randomized to the MEDD group will be assigned to the Medifast AchieveTM Plan (4 & 2 & 1 Plan"') for weight loss. Study-specific printed materials (including the "Getting Started Instructions"), will be dispensed at Visit 2 (week 0) along with a starter meal kit containing approximately one week's worth of study foods (see Supplementary Materials). Participants will place an order for the following four weeks' worth of study foods with additional study foods ordered throughout the study. Following the clinic visit, participants randomized to this group will be instructed to contact the Medifast Nutrition Support Team by telephone prior to 17:00 h EST to receive an overview of the weight loss program. This telephone call (10-15 min in length) will take place the day of Visit 2 (week 0) as participants will be instructed to start their weight loss program on the day following the randomization visit (day 1). Participants will also have telephone and e-mail access to the Medifast Nutrition Support Team (at the participants' discretion) and Medifast online tools throughout the study. Participants in the MEDD group will be encouraged to track weight and food intake and access MEDD written, online, and virtual support tools to use at their discretion. More details on the MEDD program can be found in Section 6.4.1.

Clinic Visits (Visit 3, 4, 5, 6 and 7; weeks 2, 4, 8, 12, and 16)

At Visit 3 (week 2), participants will arrive at the clinic fasted $(12 \pm 2 h, water only, anchored to time of gown body weight measurement) to undergo clinic visit procedures (evaluations of inclusion/exclusion criteria, concomitant medication/supplement use, vital signs, and AEs). Gown body weight will be measured.$

At Visit 4 (week 4), participants will arrive at the clinic fasted $(12 \pm 2 \text{ h})$, water only, anchored to time of gown body weight measurement) to undergo clinic visit procedures (evaluations of inclusion/exclusion criteria, concomitant medication/supplement use, vital signs, and AEs). Gown body weight and body circumferences [waist, hip, chest, upper arm (dominant arm), and thigh (dominant leg)] will be measured. Additionally, female participants <60 years of age will undergo an in-clinic urine pregnancy test. A DXA scan will be performed (female participants <60 years of age must have a negative pregnancy test before the DXA scan is initiated). All participants will then be administered the Program Questionnaire (Appendix 5), and TSFL and MEDD participants will place an order for the following four weeks' worth of study foods.

At Visit 5 (week 8), participants will arrive at the clinic fasted $(12 \pm 2 \text{ h}, \text{water only}, \text{anchored to time of gown body weight measurement}) to undergo clinic visit procedures (evaluations of inclusion/exclusion criteria, concomitant medication/supplement use, vital signs, and AEs). Gown body weight and body circumferences [waist, hip, chest, upper arm (dominant arm), and thigh (dominant leg)] will be measured. Additionally, female participants <60 years of age will undergo an in-clinic urine pregnancy test. A DXA scan will be performed (female participants <60 years of age must have a negative pregnancy test before the DXA scan is initiated). Participants will then be administered the IWQOL-Lite and the RAND-36 Questionnaires. All$

participants will then be administered the Program Questionnaire, and TSFL and MEDD participants will place an order for the following four weeks' worth of study foods.

At Visit 6 (week 12), participants will arrive at the clinic fasted $(12 \pm 2 \text{ h})$, water only, anchored to time of gown body weight measurement) to undergo clinic visit procedures (evaluations of inclusion/exclusion criteria, concomitant medication/supplement use, vital signs, and AEs). Gown body weight and body circumferences [waist, hip, chest, upper arm (dominant arm), and thigh (dominant leg)] will be measured. Additionally, female participants <60 years of age will undergo an in-clinic urine pregnancy test. A DXA scan will be performed (female participants <60 years of age must have a negative pregnancy test before the DXA scan is initiated). All participants will then be administered the Program Questionnaire, and TSFL and MEDD participants will place an order for the following four weeks' worth of study foods.

At Visit 7 (week 16), participants will arrive at the clinic fasted $(12 \pm 2 \text{ h}, \text{water only}, \text{anchored}$ to time of gown body weight measurement) to undergo clinic visit procedures (evaluations of inclusion/exclusion criteria, concomitant medication/supplement use, vital signs, and AEs). Blood samples will be collected for analysis ofhs-CRP, with additional blood samples collected and archived for possible future analysis of non-genetic indicators of inflammation and metabolism. Gown body weight and body circumferences [waist, hip, chest, upper arm (dominant arm), and thigh (dominant leg)] will be measured. Additionally, female participants <60 years of age will undergo an in-clinic urine pregnancy test. A DXA scan will be performed (female participants <60 years of age must have a negative pregnancy test before the DXA scan is initiated). Participants will then be administered the IWQOL-Lite, the RAND-36, the Program Questionnaire, and the Satisfaction and Health/Well-being Questionnaire (Appendices 3, 4, 5, and 6). All study participants will be dispensed maintenance handouts and guides prior to discharge from the clinic (see Supplementary Materials). Additionally, eligible Control group participants will be given instructions for placing orders for study food upon completion of all study visits.

					-				
·		ening/ eline	Clinic Visits						
lvisit'	1	2	3	4	5	6	7		
Week	-1	0	2	4	8	12	16		
Infon; ed Consent/I-iiPAA ²	X								
Demographics/Medical History	X								
Clinic Visit'	X	X	Х	Х	X	X	X		
Gown Body Weight	X	Х	Х	Х	X	X	Х		
Anthropometries'		Х		Х	X	X	X		
In-clinic Urine Pregnancy T st ⁵	X	Х		Х	X	X	Х		
Chemistry Profile ⁶	Х								
Hematology Panel ⁷	X]			
-h,;-:CRP ⁸		Х				_	X		
Archive Blood Samples ⁹		Х					Х		
Randomization		Х							
Dual Energy X-ray Absorptiometry		Х		X	X	X	Х		
IWQOL-Lite Questionnaire'''		X			X		Х		
-RAND-36"		Х			X		Х		
)iet Education"		Х							
Dispense Educational Material "		Х							
Dispense Study Food ¹⁴		Х							
Order Study Food ¹⁵		Х		X	X	X	X		
Program QuestJOnnatre ¹⁶		X		Х	Х	X	X		
Dispense Maintenance Guidc ¹⁷							X		
Satisfaction and Health/Well-being Questionnaire"							X		

Footnotes:

¹A window of 1-14 d will be allowed between Visits 1 and 2. A window of ± 2 d will be allowed between clinic visits 2 and 3. All other clinic visits will have $a \pm 3$ day window (Visit 3 through 7).

'Health Insurance Portability and Accountability Act (HIPAA). The signed document authorizes the use and disclosure of the participant's Protected Health Information by the Clinical Investigator and staff solely for the purposes of the study.

³ Clinic visit procedures include evaluations of height (Visit I, week -I only), BMI calculation (Visit 1 and 2, weeks -1 and 0 only), vital signs, inclusion/exclusion criteria (for eligibility at Visit 1 and for potential protocol deviations at subsequent visits), concomitant medication/supplement use, and AEs, where appropriate.

⁴Body circumference measurements (waist, hip, chest, dominant thigh, and dominant upper arm; Appendix 2).

⁵Urine pregnancy tests will be completed for all women< 60 years of age.

⁶The following will be performed as a part of the fasting (12 h \pm 2 h, water only) chemistry panel: glucose, calcium, albumin, total protein, sodium, potassium, carbon dioxide (CO₂), chloride, blood urea

Confidential

nitrogen (BUN), creatinine, alkaline phosphatase (ALP), aminotransferase (AST), alanine aminotransferase (ALT), total bilirubin, and osmolality.

⁷The following will be performed as part of the fasting $(12 \text{ h} \pm 2 \text{ h}, \text{water only})$ hematology measurements: white blood cell count/automated differential, red blood cell count, hemoglobin, hematocrit, platelet count, mean corpuscular volume, mean corpuscular hemoglobin, and mean corpuscular hemoglobin concentration.

⁸Blood will be collected for analysisofhs-CRP.

⁹Blood will be collected and archived for possible future analysis of non-genetic indicators of inflammation and metabolism.

¹⁰Appendix 3.

"Appendix 4.

 12 AII three groups will receive diet instructions at Visit 2 (week 0). See Section 6.4.1 for details. JJAII three groups will receive educational materials at Visit 2 (week 0). See Section 6.4.1 for details.

¹⁴The TSFL group and the MEDD group will receive study food as part of the study program. See Section 6.4.1 for details.

¹⁵The TSFL group and the MEDD group will place orders for additional study foods with the study staff at visits 2, 4, 5, and 6 (weeks 0, 4, 8, and 12); these will be shipped directly from Medifast. Orders must be submitted on the visit days. Participants who are assigned to the Control group and complete all study visits will be provided instructions for placing orders for study food at Visit 7 (week 16). "Appendix 5.

¹⁷All study groups will receive handouts with guidance for weight maintenance.

¹⁸Appendix 6.

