
(Circle One Number)

Not at all 1

A little bit 2

Moderately 3

Quite a bit 4

Extremely 5

These questions are about how you feel and how things have been with you **during the past 4 weeks.** For each question, please give the one answer that comes closest to the way you have been feeling.

How much of the time during the past 4 weeks

Participant's Initials

Date

(Circle One Number on Each Line)

	All of the Time	Most of the Time	A Good Bit of the Time	Some of the Time	A Little of the Time	None of the Time
23. Did you feel full of pep?	1	2	3	4	5	6
24. Have you been a very nervous person?	1	2	3	4	5	6
25. Have you felt so down in the dumps that nothing could cheer you up?	1	2	3	4	5	6
26. Have you felt calm and peaceful?				4	5	6
27. Did you have a lot of energy?				4	5	6
28. Have you felt downhearted and blue?				4	5	6
29. Did you feel worn out?				4	5	6
30. Have you been a happy person?				4	5	6
31. Did you feel tired?	1	2	3	4	5	6

Participant's Initials _____ Dale _____

32. During the **past 4 weeks**, how much of the time has your **physical health or emotional problems** interfered with your social activities (like visiting with friends, relatives, etc.)?

(Circle One Number)

All of the time 1

Most of the time 2

Some of the time 3

A little of the time 4

None of the time 5

How TRUE or FALSE is each of the following statements for you.

(Circle One Number on Each Line)

	Definitely True	Mostly True	Don't Know	Mostly False	Definitely False
33. ∎seem to get sick a little easier than other people	1	2	3	4	5
34. ∎am as healthy as anybody ∎ know	1	2	3	4	5
35. ∎expect my health to get worse	1	2	3	4	5
36. My health is excellent	1	2	3	4	5

Adapted fi om: Ware JE Jrl, Sherbourne CD. The MOS 36-item short-form health survey (SF-36).!. Conceptual framework and item selection. *Med Care*. 1992; 30:473-83.

Jason Pharmaceuticals) Inc. BI0-1607 (MED 019) 21 June 2016; Version 1.7 **Cm?fidential**

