Appendix 5. l'rogram Questionnaire

Visit 2	Visit 4	Visit 5	Visit 6	Visit 7
-	domization no			
Participant's	Initials	Date		

Ouestions 1 and 2 for All Groups at Visit 2 only:

- I. Describe your physical activity at work or school, on average, over the last 4 weeks?
 - **O** Very Light (sitting at your computer or desk most of the day)
 - O Light (light industrial work, sales or office work that comprises light activity)
 - **O** Moderate (cleaning, kitchen stan:or delivering mail on foot or by bicycle)
 - **O** Heavy (heavy industrial work, construction work or farming)
- 2. Describe your physical activity at leisure time, on average, over the last 4 weeks?
 - **O** Very Light (almost no activity at all)
 - O Light (walking, non-strenuous cycling or gardening approximately once a week)
 - **O** Moderate (regular activity at least once a week, e.g., walking, bicycling (including to work) or gardening)
 - **O** Active (regular activities more than once a week, e.g., intense walking, bicycling or sports)
 - **O** Very Active (strenuous activities several times a week)

Ouestions 3, 4, and 5 for All Groups to be answered at Visits 4, 5, 6, and 7:

DIRECTIONS: Please draw a single, vertical_straight, mark along the line to indicate your response. The vetiiealline must intersect with the horizontal line. Please do not circle any words. Your response should indicate how you are feeling at this moment.

3.

Over the last 4 weeks, how well did you follow your assigned weight loss plan?

Not at all

Perfectly

VAS measurement (mm):

- 4. Describe your physical activity at work or school, on average, over the last 4 weeks?
 - **O** Very Light (sitting at your computer or desk most of the day)
 - **O** Light (light industrial work, sales or office work that comprises light activity)
 - O Moderate (cleaning, kitchen staff, or delivering mail on foot or by bicycle)
 - **O** Heavy (heavy industrial work, construction work or farming)
- 5. Describe your physical activity at leisure time, on average, over the last 4 weeks?
 - **O** Very Light (almost no activity at all)
 - **O** Light (walking, non-strenuous cycling or gardening approximately once a week)
 - **O** Moderate (regular activity at least once a week, e.g., walking, bicycling (including to work) or gardening)
 - **O** Active (regular activities more than once a week, e.g., intense walking, bicycling or sports)
 - **O** Very Active (strenuous activities several times a week)

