Ouestion 6: MEDD and TSFL groups only to be answered at Visits 4, 5, 6, and 7:

6. Over the last 4 weeks, how many Medifast meal replacement products did you consume on **MOST DAYS?** (Do not count Flavors of Home meals or Medifast Snacks in your count.)

Please circle response (limit to one answer).

- 0
- •
- 2
- 3
- 4
- 5
- 6
- >6

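### The adherence VAS directions contradict the item they introduce, and meal-replacement and quality-of-life answers are collected after the clinic weigh-in with nothing withholding the reading

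*Protocol*

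**What the plan says.** Protocol Section 6.1 describes each clinic visit in sequence. At Visits 4 to 7, gown weight, circumferences, the pregnancy test where applicable and DXA come first, and the questionnaires follow. At Visit 4: "All participants will then be administered the Program Questionnaire (Appendix 5". At Visit 5: "Participants will then be administered the IWQOL-Lite and the RAND-36 Questionnaires", followed by the Program Questionnaire. At Visit 6 the Program Questionnaire again comes last. At Visit 7: "Participants will then be administered the IWQOL-Lite, the RAND-36, the Program Questionnaire, and the Satisfaction and Health/Well-being Questionnaire". The lists in Sections 6.6.4 to 6.6.7 also put gown weight ahead of the questionnaires. Section 6.5.3 describes the digital scale and says nothing on whether the participant sees or is told the reading.

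In Appendix 5, the directions above Question 3 end with "Your response should indicate how you are feeling at this moment". Question 3 itself reads "Over the last 4 weeks, how well did you follow your assigned weight loss plan". Question 6, for TSFL and MEDD only, begins "Over the last 4 weeks, how many Medifast meal replacement products did you consume on" and asks for the number on most days.

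Protocol Section 4 states an objective that uses these answers: "Relationships between changes in body weight with self-reported adherence and QoL assessments will also be examined".

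**The concern.** There are two separate problems.

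The first is a wording fault. A participant who follows the directions rates a present feeling; one who follows the question rates four weeks of behaviour. The resulting score has no single meaning. Self-reported meal replacements, coaching attendance and Nutrition Support use exist only in one or both Medifast arms, so this VAS is the only adherence measure on which Control can be set beside them.

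The second is an order effect. Participants are weighed, know which program they are on, and then report how many meal replacements they ate and how their weight affects their life. Someone who has just seen a good result may recall better intake or report better self-esteem. For the meal-replacement correlation, the outcome would then be shaping the variable set against it. For quality of life, an arm that loses more weight would more often answer after good news, which could widen the difference between arms.

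**Working it through.** No figure in the plan is in dispute, so the check is mainly of text: which instruments follow the weigh-in, what period each covers, and how the SAP uses each.

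**Recall period**
- Program Questionnaire, Questions 3 to 6: last 4 weeks. The present-moment sentence appears only in the directions above Question 3.
- RAND-36: four weeks for many items, including the block introduced by "These questions are about how you feel and how things have been with you"; other items ask about health now or in general.
- IWQOL-Lite: the past week (the extracted text is damaged here).
- Satisfaction and Health/Well-being: the whole study.

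The conflict of time frame is therefore confined to the VAS.

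**Use in the SAP (Section 9.0)**
- VAS: descriptive statistics only, shown by arm in Table 4.9.
- Meal replacements (Question 6): averaged over Visits 4 to 7 and correlated (Spearman) with absolute weight change to week 16, for TSFL and MEDD. Exposed.
- IWQOL-Lite and RAND-36: ANCOVA with intervention, sex and baseline value; no term for weight change. Exposed.
- Satisfaction: cumulative logit model with sex and absolute weight change as covariates. Largely protected against an effect that runs through weight change.
- Coaching contacts: a count of contacts, not a questionnaire answer. Not exposed.
- Body weight (primary): measured. Not exposed.

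**Baseline.** Visit 2 also weighs first. However, that reading precedes randomization and carries no news of progress, so subtracting baseline does not cancel a later effect.

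**Scale of the meal-replacement correlation (assumed values only).** The documents give no size for a weigh-in effect. Take the planned evaluable n = 55 in one arm, no true association, and a two-sided 5% test. Let ρ be the correlation that the weigh-in alone would induce. By the Fisher approximation,

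P(significant) = 1 − Φ(1.96 − z) + Φ(−1.96 − z), with z = atanh(ρ) × √(55 − 3).

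| Assumed ρ | z | P(significant) |
|---|---|---|
| 0.1 | 0.72 | 11% |
| 0.2 | 1.46 | 31% |
| 0.3 | 2.23 | 61% |
| 0.4 | 3.05 | 86% |

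The formula is for a Pearson correlation, so it is approximate for Spearman. The table shows what would follow if such an effect existed; it is not evidence that one does. ρ also mixes clinic and home knowledge of weight, so it does not measure what reordering would remove.

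**Items before weighing if the order is reversed**
- Visit 7: 31 (IWQOL-Lite) + 36 (RAND-36) + 3 or 4 (Program Questionnaire) + 20 (Satisfaction) = 90 or 91.
- Visit 5: 31 + 36 + 3 or 4 = 70 or 71.
- Visits 4 and 6: 3 or 4.
- Visit 2: 31 + 36 + 2 = 69.

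**The case against.** The strongest reply is that the exposure is inferred from silence and the consequences are limited. No passage says participants are told their weight. Circumferences, a pregnancy test for women under 60 and a DXA scan come between weighing and answering. TSFL and MEDD participants are encouraged to track their weight, so the clinic reading may tell them little. A product count leaves less room for mood than a rating does. The lists in Section 6.6 are weak evidence of sequence, since 6.6.2 lists randomization ahead of the baseline weight.

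Most of this stands. It makes the order effect a possibility of unknown size and means reordering would remove only part of it. It does not remove the possibility: Section 6.1 alone sets the order, and a participant standing on a digital scale can ordinarily read it unless someone prevents that.

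A reader might infer more from the Section 4 objective, namely that reported correlations of weight change with the adherence rating or with quality of life would be inflated. The SAP plans neither correlation. A reader might also infer inflated differences between arms in satisfaction. That model already adjusts for weight change, and items such as whether the plan worked may properly depend on weight lost.

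None of this answers the Appendix 5 conflict, which is plain on the page.

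**Conclusion.** The point holds as a minor to moderate issue for secondary outcomes. The contradiction between the VAS directions and Question 3 is certain and affects a listed secondary outcome, although one that the SAP only summarises. The order effect is plausible and unquantified. It bears on the meal-replacement correlation and on the IWQOL-Lite and RAND-36 comparisons. It rests on two assumptions the documents neither confirm nor exclude: that participants learn the clinic reading before answering, and that it changes some answers.

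The documents do not support the broader reading that adherence, quality-of-life and satisfaction answers all reflect the day's weight in place of the past four weeks. IWQOL-Lite and Satisfaction do not use a four-week period, and RAND-36 does so only in part. The measured primary outcome is untouched.

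**What to change.** 1. In Appendix 5, delete the sentence "Your response should indicate how you are feeling at this moment". The VAS then refers only to the last four weeks. This costs nothing beyond the wording change.

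2. In Sections 6.1 and 6.6, choose one of two routes.
   - Give the questionnaires before the gown weight, circumferences and DXA. The same electronic instruments, visits and staff are used. The cost is time before a fasted weigh-in: 90 or 91 items at Visit 7, to be scheduled within the 12 ± 2 h fast that is anchored to weighing. If Visit 2 is reordered too, so that baseline and follow-up are answered under the same conditions, its 69 items must also fit ahead of randomization before 12:00 h.
   - Keep the present order and state that the weight and DXA results are not shown or told to the participant until the questionnaires are completed. This avoids the scheduling cost and needs only an instruction to staff.

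Neither route removes what participants already know from weighing themselves at home, so the study report should say that these self-reports were given by participants who knew their arm and may have known their weight.
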